## 8.3. Analysis Methods

### 8.3.1. Primary Effectiveness Endpoint

The primary effectiveness endpoint of this study maps to the primary efficacy objective and addresses the following research question:

*At 90 days ( $\pm 15$  days) following the study index procedure, is the lower bound of the 1-sided 95% confidence interval of the difference (Envi™-SR minus Control) in global disability ( $mRS \leq 2$ ) above the a priori threshold of -12.5%? This is a 1-sided evaluation to establish non-inferiority.*

The hypothesis is that the proportion of good outcomes ( $mRS \leq 2$ ) at 90 days after treatment with the Envi™-SR thrombectomy device in patients with cerebral infarction is non-inferior to the rate of good outcome at 90 days after treatment with the Control device. The largest clinically acceptable effect to be able to declare non-inferiority is -12.5% (non-inferiority margin). The null and alternative hypotheses can be defined mathematically as follows:

- Ho: Treatment with Envi™-SR is inferior to treatment with Control for good outcomes defined as an  $mRS \leq 2$  at 90 days based on a non-inferiority margin of -12.5% (good outcome with Envi™-SR  $<$  [good outcome with Control – 12.5%]).

- Ha: Treatment with Envi™-SR is non-inferior to treatment with Control for good outcome defined as an mRS  $\leq 2$  at 90 days based on a non-inferiority margin of -12.5% (good outcome with Envi™-SR  $\geq$  [good outcome with Control – 12.5%])

The SAS code to generate these summary statistics and addressing missing mRS data at 90 days post-procedure is presented in the Statistical Analysis Plan. If the lower bound of the 1-sided 97.5% confidence interval of the difference (Envi™-SR minus Control) in global disability is numerically greater than -12.5%, Envi™-SR will be considered non-inferior to Control.

Additional therapies are defined in Section 3.5. The primary effectiveness endpoint will be derived 3 ways:

Method 1: mRS based on the observed results, independent of the use of additional therapies to retrieve the clot. Multiple imputation will be used to impute the mRS score for patients who become lost to follow-up prior to the 90 day evaluation.

Method 2: mRS based on the observed results for patients where additional therapies were not used to retrieve the clot. Subjects who required additional therapy for reperfusion failure or additional off-label therapies to retrieve the clot will be automatically treated as primary effectiveness endpoint failures. Multiple imputation will be used to impute the mRS score for patients who become lost to follow-up prior to the 90 day evaluation.

Method 3: mRS based on the observed results for patients where additional therapies were not used to retrieve the clot. Subjects who required any additional therapy to retrieve the clot will be automatically treated as primary effectiveness endpoint failures. Multiple imputation will be used to impute the mRS score for patients who become lost to follow-up prior to the 90 day evaluation.

An important consideration in requiring any patient who received additional therapy to retrieve the clot is acknowledging this is truly a random effect. The observed mRS at 90 days could indicate no difference in functional independence between the 2 randomized treatment groups, but the use of additional therapies could, by chance and chance alone, result in non-inferiority being achieved or lost. For this reason, Method 1 is the primary method for the derivation of the primary effectiveness endpoint for the study; Method 2 and Method 3 represent secondary derivations of the primary effectiveness endpoint.

Two (2) additional sensitivity analyses will be prepared to explore alternative methods for imputation for patients who are lost to follow-up (ref. Section 5.4) for the primary endpoint. The first sensitivity analysis will impute the baseline value for the 90-day result, functionally resulting in no change from baseline. The second sensitivity analysis will be conducted imputing the worst score at 90-days recorded for a patient within their respective treatment group for patients who are lost to follow-up. Additional details are provided in the SAP.

Additionally, as a final sensitivity analysis of the primary endpoint, a logistic model will be performed within the imputed datasets derived using multiple imputation. This model will incorporate the stratification variables specified in the randomization as covariates and with randomization group assignment. Under the guise of a sensitivity analysis, separate sub-group analysis will be prepared to examine factors that may have influenced the 90-day mRS scores.

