-------------------	--

	
The primary effectiveness endpoint is an assessment of global disability assessed via the blinded evaluation by the assessing clinical team of the proportion of subjects with a Modified Rankin Scale (mRS) <math>\leq 2</math> recorded 90 days (<math>\pm 15</math> days) after the study index procedure. The proportions will be compared between the Envi™-SR and Control device arms. The variability between and within the five (5) peer-reviewed reference studies serves as the basis for establishing the non-inferiority margin for this endpoint.
 
The primary effectiveness endpoint will be derived three (3) ways:
 
Method 1: mRS based on the observed results, independent of the use of additional therapies to retrieve the clot. Multiple imputation will be used to impute the mRS score for patients who become lost to follow-up prior to the 90 day evaluation.
 
Method 2: mRS based on the observed results for patients where additional therapies were not used to retrieve the clot. Patients who required additional therapy for reperfusion failure or additional off-label therapies to retrieve the clot will be automatically treated as primary effectiveness endpoint failures. Multiple imputation will be used to impute the mRS score for patients who become lost to follow-up prior to the 90 day evaluation.
 
Method 3: mRS based on the observed results for patients where additional therapies were not used to retrieve the clot. Subjects who required any additional therapy, either on label or off-label, to retrieve the clot will be automatically treated as primary effectiveness endpoint failures. Multiple imputation will be used to impute the mRS score for patients who become lost to follow-up prior to the 90 day evaluation.
 
Method 1 is the primary method for the derivation of the primary effectiveness endpoint for the study; Method 2 and Method 3 represent secondary derivations of the primary effectiveness endpoint.
 
The non-inferiority margin for the primary effectiveness endpoint has been pre-specified at 12.5%. The primary effectiveness analysis will be based on the lower bound of the 1-sided 97.5% confidence interval of the difference (Envi™-SR minus Control) in global disability. If the lower bound is numerically greater than -12.5%, Envi™-SR will be considered non-inferior to Control.
 
The primary safety endpoint is an assessment of device-related or procedure-related symptomatic intracranial hemorrhage (sICH) within 24 hours (-8/+12 hours) (as read by the Core Lab and adjudicated by CEC) of the study index procedure. The incidence of sICH is not expected to exceed 4% in either arm of the study. If the upper bound of the 1-sided 97.5% confidence interval of the difference (Envi™-SR minus Control) in sICH is numerically less than 7%, Envi™-SR will be considered non-inferior to Control.

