### 8.2. Sample Size Considerations

The objective of this trial is to demonstrate similar performance after treatment with the Envi™-SR device compared to the expected proportion of good outcomes at 90 days in the Control arm. The expected proportion of good outcomes in the Envi™-SR arm was estimated based on earlier results with Control. A -12.5% non-inferiority margin (NIM) will be used to examine the lower bound of the 1-sided 97.5% exact binomial confidence interval of the difference (Envi™-SR minus Control) in the proportion of patients with a 90-day mRS of 0-2. The null hypothesis and alternative hypothesis are presented below.

Ho: Envi™-SR – Control  $\leq$  -12.5%

Ha: Envi™-SR – Control  $>$  -12.5%

If the lower bound of the 1-sided 97.5% exact binomial confidence interval of the difference (Envi™-SR minus Control) in the proportion of patients with a 90-day mRS of 0-2 is greater than -12.5%, then non-inferiority will be established.

The planning estimates for the Envi™-SR study considered the lower bound of the 2-sided 95% (asymptotic) confidence interval from the SWIFT PRIME study for estimation (50.5%). Sample size estimates were prepared for this parallel design study assuming a non-inferiority margin of -12.5% (Envi™-SR successes [%] minus Control successes [%]). Under the alternative hypothesis, non-inferiority would be claimed if the lower bound of the 1-sided 97.5% confidence interval of the difference is less than the non-inferiority margin of -12.5%. All planning estimates are performed for the ITT population as this is the primary population for analysis.

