### Maximum Sample Size

If the gap narrows between the 2 randomized groups to 49.5% (Control) and 50.5% (Envi™-SR), 426 total patients (ITT) will be required (type 1 error rate of 2.5%, power of 80%). A loss to follow-up rate of 5% or less is expected. Missing data will be imputed as described in section 8.2.2. As multiple imputation could dampen the signal from the subject data that is imputed, an additional 5% of subjects may be added to compensate for any potential impact, leading to a total sample size of 448 subjects (ITT).

All estimates are performed based on the ITT population. However, all enrolled subjects (i.e., consented), including enrolled screen failures, will count toward the maximum sample size of 560 patients. The rate of enrolled screen failures is not expected to exceed 25%. Therefore, the maximum sample size for enrollment will be the ITT maximum sample size plus 25%, or 560 patients.

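### The primary non-inferiority rule is stated at two confidence levels and in two opposite directions, so near-margin results have no single verdict

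*Combined protocol and SAP*

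**What the plan says.** The primary comparison is the difference in the proportion with 90-day mRS 0-2, Envi-SR minus Control, against a margin of 12.5 points. The protocol states the success rule five times.

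- **Synopsis, Statistics.** The analysis rests on the "lower bound of the 1-sided 97.5% confidence interval of the difference (Envi™-SR minus Control) in global disability", and the direction is given as "If the lower bound is numerically greater than -12.5%, Envi™-SR will be considered non-inferior to Control".
- **Section 8.2, after the hypotheses.** A 1-sided 97.5% exact binomial interval is specified. If its lower bound for the difference in patients "with a 90-day mRS of 0-2 is greater than -12.5%, then non-inferiority will be established".
- **Section 8.2, next paragraph.** Here "non-inferiority would be claimed if the lower bound of the 1-sided 97.5% confidence interval of the difference is less than the non-inferiority margin" of -12.5%.
- **Section 8.3.1, research question.** It asks "is the lower bound of the 1-sided 95% confidence interval of the difference (Envi™-SR minus Control) in global disability" above the -12.5% threshold.
- **Section 8.3.1, after the hypotheses.** "If the lower bound of the 1-sided 97.5% confidence interval of the difference (Envi™-SR minus Control) in global disability is numerically greater than -12.5" per cent, the device is non-inferior.

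The sizing text under Maximum Sample Size gives a "type 1 error rate of 2.5%, power of 80" per cent. The Target Sample Size paragraph, which gives 270, states neither alpha nor power.

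**The concern.** Three of the five statements agree: 1-sided 97.5% lower bound, success if greater than -12.5%. The other two do not.

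The 8.3.1 research question lowers the confidence level to 95%. That is a coherent rule in its own right, and it sits in the section that defines the primary analysis. A result between the two cut-offs passes under one sentence and fails under another a few lines later.

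The second sentence in 8.2 reverses the direction. Read literally, it passes an inferior device and fails a non-inferior one.

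Other parts of the plan depend on this threshold. The secondary endpoints are tested only if it is met. The interim conditional power, with its 37% futility limit, needs a fixed final critical value, because the same interim data give different conditional power under a 95% and a 97.5% final bound. If the text is first harmonised after outcome data are known, the choice could be seen as driven by the result.

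**Working it through.** **Inputs.** Margin 12.5 points (synopsis, 8.2). Target size: Control 46%, Envi-SR 50.5%, 270 in total, so 135 per arm. Maximum size: 49.5% and 50.5%, 426 in total, so 213 per arm, raised to 448 (224 per arm). Allocation is 1:1. Alpha of 2.5% and power of 80% are stated for the maximum size; I assume they also apply to 270.

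**Which alpha do the stated sizes imply?** With unpooled variance,

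n per arm = (z₁₋α + z₀.₈₀)² × [p_C(1-p_C) + p_T(1-p_T)] / (0.125 + p_T - p_C)²

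| Case | One-sided alpha | n per arm | Total | Stated |
|---|---|---|---|---|
| 46% v 50.5% | 0.025 | 7.849 × 0.4984 / 0.170² = 135.4, so 136 | 272 | 270 |
| 46% v 50.5% | 0.05 | 6.183 × 0.4984 / 0.170² = 106.6, so 107 | 214 | 270 |
| 49.5% v 50.5% | 0.025 | 7.849 × 0.49995 / 0.135² = 215.3, so 216 | 432 | 426 |
| 49.5% v 50.5% | 0.05 | 6.183 × 0.49995 / 0.135² = 169.6, so 170 | 340 | 426 |

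One-sided 2.5% reproduces both figures closely (270.7 before rounding for the target; 1.4% off for the maximum). One-sided 5% reproduces neither.

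**Smallest observed difference that passes.** SE = √{[p_C(1-p_C) + p_T(1-p_T)] / n}, and the cut-off is -12.5 + z × SE, in percentage points.

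- 135 per arm, 46% and 50.5%: SE = √(0.498375/135) = 6.08 points. At 97.5%: -12.5 + 1.96 × 6.08 = **-0.6**. At 95%: -12.5 + 1.645 × 6.08 = **-2.5**.
- 213 per arm, 49.5% and 50.5%: **-3.0** and **-4.5**.
- 224 per arm, 46% and 50.5%: SE = √(0.498375/224) = 4.72 points, giving **-3.3** and **-4.7**. With 49.5% and 50.5% the first figure is -3.2 and the second is unchanged.

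**Operating characteristics at 135 per arm.** These come from exact enumeration of the two binomials with an unpooled Wald bound, Control at 46%.

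| Rule | Passes at true difference -12.5 points | Passes at design alternative (50.5%) |
|---|---|---|
| 97.5% bound > -12.5% | 2.5% | 78.9% |
| 95% bound > -12.5% | 4.8% | 87.8% |
| 97.5% bound < -12.5% (reversed) | about 97% | about 21% |

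The 95% and 97.5% rules therefore disagree in 87.8 - 78.9 = 8.9% of trials at the design alternative. At 213 per arm the disagreement is about 7%.

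**The case against.** The strongest reply is that the intent is not in doubt. The 97.5%, greater-than rule appears three times, including the sentence in 8.3.1 that declares non-inferiority. The primary safety endpoint and secondary endpoints 2 to 4 use the same level, and every type I error rate stated for sizing is 2.5%. The stated Ns fit only that alpha. The synopsis also pairs 1-sided 97.5% with 2-sided 95% limits, so the 1-sided 95% may be a slip between two equivalent conventions. The *less than* sentence contradicts the hypotheses just above it, and no analyst would implement it.

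Most of this stands. The *less than* sentence is evidently a drafting error, and the intended rule can be recovered. That identifies the right correction; it does not remove the need for one. The 95% wording is not plainly a slip, since a 1-sided 95% bound is a workable rule and is stated as the formal research question. A confirmatory threshold should not have to be inferred by counting sentences.

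Three limits on the figures also stand. The 2.5% alpha for the 270 target is inferred by reproduction, not stated. The cut-offs use a Wald standard error at fixed planning rates, whereas the plan calls for an exact binomial interval and multiple imputation, so they are illustrative. The separate SAP, which the protocol cites for the SAS code, was not available in the text reviewed. It may already fix the level or may repeat the error.

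**Conclusion.** The concern holds. Current text states the primary decision rule at two confidence levels and in two directions. The 95% wording is the more serious fault: it doubles the nominal one-sided type I error from 2.5% to 5% (about 4.8% by enumeration at 135 per arm) and shifts the cut-off by about 1.9 points at 135 per arm, or about 1.5 points at 224. The reversed sentence is an obvious error but states the opposite of the trial's hypothesis.

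The figures assume the planning rates and a normal-approximation bound. The textual conflict depends on neither. The weight of the document supports a 1-sided 97.5% lower bound greater than -12.5%. Under that rule approximate power is 79.9% at 135 per arm and 79.6% at 213 per arm, so the stated 270 and 426 stand.

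**What to change.** 1. In the 8.3.1 research question, change 1-sided 95% to 1-sided 97.5%.
2. In the second statement of the rule in 8.2, change *less than* to *greater than* the margin of -12.5%.
3. State the rule once, with level, direction and interval method, and cross-refer to it from the synopsis, 8.2 and 8.3.1.
4. While editing, align the hypotheses: a difference exactly equal to the margin falls under the null in 8.2 but under the alternative in 8.3.1. The practical effect is negligible.
5. Check the separate SAP, its code and the DMC's conditional-power specification for the same level and direction.

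The cost is a short wording amendment. Sample size, design and patient numbers do not change. It should be made before any comparative outcome data are seen.

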### 8.3.2. Analysis of the Secondary and Tertiary Endpoints

If non-inferiority is achieved based on the primary endpoint, a hierarchical step-down approach will be used to test the secondary endpoints in rank order. The following secondary effectiveness endpoints will be compared between the two treatment arms:

1. The first secondary effectiveness endpoint will be an assessment of the mRS shift from baseline at 90 days ( $\pm 15$  days) following the study index procedure. The Cochran–Mantel–

Haenszel test will be used to derive the 95% confidence intervals for the overall odds ratio. If the 95% confidence intervals for the overall odds ratio does not contain 1, the conclusion will be that the mRS shift is not proportional between the 2 devices. This is a 2-sided evaluation of the odds ratio.

2. The second secondary effectiveness endpoint will be an assessment of the proportion of patients who achieve reperfusion measured using the expanded Thrombolysis in Cerebrovascular Infarction index (eTICI). Successful achievement of the endpoint is defined as achieving an eTICI score of 2b50 or greater [eTICI 2b50-3] in the target vessel following three or less passes of the randomized device (as adjudicated by Core Lab). If the lower bound of the 1-sided 97.5% confidence interval of the difference (Envi™-SR minus Control) in the proportion of patients with eTICI 2b50 or greater flow in the target vessel post-procedure is numerically greater than -12.1%, Envi™-SR will be considered non-inferior to Control. This is a 1-sided evaluation to establish non-inferiority.
3. The third secondary effectiveness endpoint will be an assessment of the proportion of patients in whom a successful First Pass Effect is achieved. Successful achievement of the endpoint is defined as achieving an eTICI First Pass Effect (FPE) defined as eTICI 2c-3 after a single pass (as adjudicated by Core Lab). If the lower bound of the 1-sided 97.5% confidence interval of the difference (Envi™-SR minus Control) in the proportion of patients with eTICI 2c or greater flow in the target vessel post- first pass is numerically greater than -12.1%, Envi™-SR will be considered non-inferior to Control. This is a 1-sided evaluation to establish non-inferiority.
4. The fourth secondary effectiveness endpoint will be an assessment of the proportion of patients in whom a successful Modified First Pass Effect is achieved. Successful achievement of the endpoint is defined as achieving an eTICI Modified First Pass Effect (mFPE) defined as eTICI 2b50-3 after a single pass (as adjudicated by Core Lab). If the lower bound of the 1-sided 97.5% confidence interval of the difference (Envi™-SR minus Control) in the proportion of patients with eTICI 2b50 or greater flow in the target vessel post- first pass is numerically greater than -12.1%, Envi™-SR will be considered non-inferior to Control. This is a 1-sided evaluation to establish non-inferiority.
5. The fifth secondary effectiveness endpoint will be an assessment of the proportion of subjects with Early Response defined as a NIHSS drop of  $\geq 10$  points from baseline or NIHSS score 0 or 1 at seven (7) days (-2/+3 days) or discharge, whichever is sooner. If the probability value from the 2-tailed Fisher's exact test is  $< 0.05$  and the proportion of patients with an NIHSS of 0 or 1, or improvement in the NIHSS of 10 points or more from the baseline (pre-procedure) score is greater in the Envi™-SR treatment arm compared to the control arm, the null hypothesis will be rejected and Envi™-SR will be considered superior to Control. This is a 2-sided evaluation of the proportions.

The details for analyzing the individual tertiary endpoints are presented in the SAP.

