Exclusion Criteria	
 
1. Life expectancy likely less than six (6) months.
 
2. Females who are pregnant or breastfeeding.
 
3. Known history of severe allergy (more than rash) to contrast medium that cannot be medically controlled.
 
4. Suspicion of renal failure (Renal failure as defined by a serum creatinine >3.0 mg/dL (264 µmol/L) or Glomerular Filtration Rate (eGFR) <30).
 
5. Severe, sustained hypertension (Systolic Blood Pressure >185 mmHg or Diastolic Blood Pressure >110 mmHg) NOTE: If the blood pressure can be successfully reduced and maintained at the acceptable level using medication the subject can be enrolled.
 
6. Currently participating in another interventional (drug, device, etc.) research project that may confound the results of this study.
 
7. Known hereditary or acquired hemorrhagic diathesis, coagulation factor deficiency. (A subject without history or suspicion of coagulopathy does not require INR or prothrombin time lab results to be available prior to enrollment.)
 
8. Known history of platelet count <100,000/µL.
 
9. Baseline blood glucose of <50mg/dL (2.78 mmol) or >400mg/dL (22.20 mmol).
 
10. Subjects with occlusions in multiple vascular territories (e.g., bilateral anterior circulation, or anterior/posterior circulation).
 
11. CT or MR evidence of hemorrhage.
 
12. Seizures at stroke onset.
 
13. Suspicion of aortic dissection.
 
14. Patients with known hypersensitivity to nickel-titanium.
 
15. Evidence of dissection in the extra or intracranial cerebral arteries.
 
16. Stenosis, or any occlusion, in a proximal vessel that requires treatment or prevents access to the site of occlusion.
 
17. Presumed septic embolus, suspicion of bacterial endocarditis, or other serious infection.
 
18. Suspected cerebral vasculitis based on medical history and CTA/Magnetic Resonance Angiogram (MRA).
 
19. Excessive vascular access tortuosity that will likely prevent endovascular access.
 
20. Baseline CT or Magnetic Resonance Imaging (MRI) showing intracranial tumor (except asymptomatic small meningiomas less than three (3) cm).
 
21. Significant mass effect with midline shift
 
22. Treatment with any cleared thrombectomy devices or other intra-arterial (neurovascular) therapies three months prior to use of treatment device
 
23. Unlikely to be available for 90-day (± 15 days) follow-up (e.g. no fixed home address, visitor from overseas).
 
24. Rapid neurological improvement prior to study enrollment suggesting resolution of signs/symptoms of stroke such as a decrease that leads to an NIHSS below the study cut-off of six (6).
 
25. Patient has suffered a hemorrhagic or ischemic stroke or TIA in at least the last three (3) months.
 
26. Patients with a pre-existing neurological or psychiatric disease that would confound the neurological or functional evaluations, mRS score at baseline must be ≤ 2. This excludes patients who are severely demented, require constant assistance in a nursing home type setting or who live at home but are not fully independent in activities of daily living (toileting, dressing, eating, cooking and preparing meals, etc.).
 
27. Known cancer with metastases.
 
28. Subject currently uses or has a recent history of illicit drug(s), which includes marijuana.
 
29. Recent past history (within three (3) months) or clinical presentation of intracranial hemorrhage (ICH), subarachnoid hemorrhage (SAH), ruptured arteriovenous malformation (AVM) or ruptured aneurysm.
 

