#### **6.8.2.3. Neurologic Evaluation**

Screening NIHSS should be recorded as performed. At screening, a pre-stroke mRS will be obtained from the subject or the subject's caretaker.

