## 6.8.10. Schedule of Events Summary Table

Study Requirement	Screening	Procedure	Post Procedure				
	Within 24 hrs. of stroke onset	Time 0	24 Hours (-8/+12)	7 Day (-2/+3) or Discharge 	30 Day (±14) 	90 Day (±15) 	Unscheduled
Informed consent	X 						
Pregnancy test	X 						
NIHSS Score	X		X 	X 			
Modified Rankin Scale (mRS)	X 				X	X 	X
Medical history	X						
Physical examination	X			X 			
Blood Pressure and Pulse	X						
Assess/confirm study eligibility	X						
Cerebral Imaging (CT or MRI)	X 		X 				
Hemoglobin and Platelet Count	X 						
Serum Glucose	X 						
Serum Creatinine or eGFR	X 						
INR, aPTT	X 						
Angiography	X 	X 					
Randomization		X					
Mechanical thrombectomy		X					
Concomitant medications	X			X	X	X	X
Record adverse events 	X	X	X	X	X	X	X

(1) Patient or Legally Authorized Representative must sign informed consent prior to screening specific tests which are beyond the local standard of care.

(2) Per institutional standard of care, for females of childbearing potential, subjects must have a documented negative pregnancy test prior to device insertion except in the case of local regulations and ethic committee approvals requiring consent post the emergency situation.

(3) Pre-ictus (Latin for Stroke)

(4) Record all adverse events from the time of signature of the ICF.

(5) To be performed at 7 days (-2/+3 days) or at discharge (whichever occurs first).

(6) Perform baseline to verify the angiographic inclusion/exclusion criteria are met.

(7) Perform angiography after every device pass, and after each additional therapy device pass. Obtain a final angiogram at the end of the interventional procedure.

(8) Assessed by blinded and certified study team member, mRS per the RFA-A.

(9) Visit may be conducted by telemedicine if clinical visit not possible.

(10) Physical exam to be conducted per institution standard of care

(11) If required per local standard of care or inclusion/exclusion criteria

(12) Per institutional standard of care. MRI with DWI is preferred, CT is acceptable. It is preferred that the same imaging modality is used at 24 hour timepoint as at baseline (CT or MRI) to make direct comparison easier.

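### Secondary endpoint 1 (mRS shift from baseline) has only a pre-stroke baseline and a Cochran-Mantel-Haenszel odds ratio with no cut-point, strata or ordinal estimator; as written, neither the score nor the estimate is properly defined

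*Combined protocol and SAP*

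**What the plan says.** The synopsis, Section 3.2 and Section 8.3.2 all word the endpoint the same way: "The first secondary effectiveness endpoint will be an assessment of the mRS shift from baseline at 90 days". None of them defines the shift further.

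The baseline value is described in three places:
- Section 6.8.2.3: "At screening, a pre-stroke mRS will be obtained from the subject or the subject's caretaker".
- The footnote to the screening mRS in the schedule of events (Section 6.8.10): "Pre-ictus (Latin for Stroke".
- Exclusion criterion 26: "mRS score at baseline must be ≤ 2".

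No mRS is taken between stroke onset and the procedure. The next scheduled score is at 30 days. Appendix A scores death as 6.

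For the analysis, Section 8.3.2 says that the Cochran-Mantel-"Haenszel test will be used to derive the 95% confidence intervals for the overall odds ratio", adds "This is a 2-sided evaluation of the odds ratio", and gives the decision rule: "If the 95% confidence intervals for the overall odds ratio does not contain 1, the conclusion will be that the mRS shift is not proportional". It states no cut-point, no stratification variables, no scores and no model.

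**The concern.** Two separate things are left open at the first step of the secondary hierarchy.

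**The score.** In plain words, a shift from baseline is the day-90 value minus the baseline value. If the baseline is the pre-stroke mRS, the same death gets a different score according to how well the patient was before the stroke. The mRS makes death the worst state for everyone. A change score that is not stratified by pre-stroke mRS does not keep that order.

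**The estimate.** A Mantel-Haenszel common odds ratio is built from one 2x2 table per stratum. The endpoint has more than two levels, whether it is read as a change score or as the 90-day mRS. Until a cut-point or an ordinal estimator is named, several odds ratios are possible and the plan does not say which one is tested.

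At stake are the meaning and reproducibility of the first secondary result, and the room left to choose score, cut and model after the data are seen.

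**Working it through.** The documents give no sample size, power or effect size for this endpoint, so there is no stated figure to reproduce.

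**Inputs from the documents:** pre-stroke mRS b = 0, 1 or 2 (eligibility criteria); 90-day mRS m = 0 to 6 with death = 6 (Appendix A); 90-day mortality about 13.8% (Section 8.2, additional estimates).

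**Assumed, because the documents do not give them:** pre-stroke mRS 0/1/2 = 75/15/10%, with a range from 90/7/3% to 50/30/20%; 90-day mRS 0 to 6 = 12/17/19/15/14/9.2/13.8%; b independent of m.

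**Step 1. The literal score, shift = m - b.**

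| Pre-stroke mRS | m=0 | 1 | 2 | 3 | 4 | 5 | 6 (dead) |
|---|---|---|---|---|---|---|---|
| 0 | 0 | 1 | 2 | 3 | 4 | 5 | 6 |
| 1 | -1 | 0 | 1 | 2 | 3 | 4 | 5 |
| 2 | -2 | -1 | 0 | 1 | 2 | 3 | 4 |

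The score has nine levels (-2 to +6), so there are eight possible cut-points.

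**Step 2. Deaths against survivors.** There are 3 x 3 x 6 = 54 pairings of a death (3 pre-stroke values) with a survivor (3 pre-stroke values, 6 outcomes).
- Ties (3): death from 1 with survival 0 to 5 (both +5); death from 2 with survival 0 to 4 (both +4); death from 2 with survival 1 to 5 (both +4).
- Reversals (1): death from 2 (+4) ranks better than survival 0 to 5 (+5).

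This step needs no distributional assumption.

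**Step 3. How often.** Survivors are 86.2% of subjects. Among them, mRS 4 has share 14/86.2 = 0.1624 and mRS 5 has share 9.2/86.2 = 0.1067.
- Ties: 0.15 x 0.75 x 0.1067 + 0.10 x 0.75 x 0.1624 + 0.10 x 0.15 x 0.1067 = 0.0120 + 0.0122 + 0.0016 = 0.0258, or 2.6% of all death/survivor pairs.
- Reversals: 0.10 x 0.75 x 0.1067 = 0.0080, or 0.8%.

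| Pre-stroke mix 0/1/2 | Tied | Reversed |
|---|---|---|
| 90/7/3% | 1.1% | 0.3% |
| 75/15/10% | 2.6% | 0.8% |
| 50/30/20% | 3.9% | 1.1% |

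A second assumed outcome distribution (14/19/17.5/14/14/7.7/13.8%), with pre-stroke mixes from 80/15/5% to 34/33/33%, gave 1.8-3.8% tied and 0.4-1.0% reversed.

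**Step 4. The other readings.** Ranking m itself, or comparing m - b only within a fixed b, gives 0 ties and 0 reversals, because death is then always the highest value.

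**Step 5. The odds ratio.** For a 2x9 ordinal table the Cochran-Mantel-Haenszel procedure gives a chi-square for mean score or association, not an odds ratio. To see whether the cut matters, take two invented arms whose outcome distributions cross (14/19/17.5/14/14/7.7/13.8% and 10/17/23.5/18/10/3.5/18%), with pre-stroke mix 70/20/10%. The odds ratios at the eight cuts, from -2 upward, are 1.41, 1.32, 1.29, 1.18, 0.97, 0.89, 1.06 and 1.35. The arms were chosen to cross, so this shows dependence on the cut, not an expected size.

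**Step 6. Error rate and power.** A rank test simulated under the Step 3 assumptions (4,000 trials per setting, proportional-odds alternative) held a two-sided error of about 5% with either score. With the 75/15/10% mix, power fell from 68% to 64% (135 per arm, odds ratio 1.7) and from 79% to 74% (213 per arm, odds ratio 1.6) when the change score replaced the 90-day mRS. Losses over the range of mixes were about 2 to 7 points. The odds ratios are assumptions.

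**The case against.** The best reply is that nobody meant a subtraction. In stroke trials a shift analysis usually means an ordinal comparison of the 90-day mRS, and the word proportional in the decision rule points that way. Cochran-Mantel-Haenszel is also a stratified method, so a comparison within pre-stroke mRS is possible. Under either reading the ordering problem is gone.

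This reply stands in part. A reader might infer that deaths will outrank survivors in this trial. The documents do not establish that; it follows only from the unstratified change-score reading. But no section states either of the other readings. Section 8.3.1 describes imputing the baseline value at day 90 as no change from baseline, so within-subject change is the plan's own usage. Pre-stroke mRS is not among the six randomisation factors, and no strata are named.

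A reader might also infer that the endpoint hides a mortality difference. It does not: stroke-related and all-cause mortality at 90 days are separate safety endpoints by arm, all deaths are adjudicated, and a death fails the primary endpoint.

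It is also tempting to quote the affected share among survivors at mRS 4-5 only (9.6% tied and 3.0% reversed in the base case). That denominator is selective. Over all death/survivor pairs the shares are those in Step 3.

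Finally, the detail might sit in a separate SAP. The text under review contains none for this endpoint. Section 8.3.2 states the method itself and passes only the tertiary endpoints to the SAP.

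**Conclusion.** The point holds as a gap in the definition of the first secondary endpoint.

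The ordering fault is certain under the literal reading (3 ties and 1 reversal in 54 pairings) but small in effect: about 2.6% of death/survivor pairs tied and 0.8% reversed, with ranges of about 1-4% and 0.3-1.1%. Those shares rest on an assumed pre-stroke mix, an assumed outcome distribution and independence of the two; only the 13.8% mortality comes from the plan. Type I error is not affected.

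The estimator gap does not depend on the reading. Both the change score and the 90-day mRS have more than two levels, and no cut-point, strata or ordinal estimator is named. It would go too far to say that the interval cannot be computed at all. A proportional-odds model, a generalised Mantel-Haenszel estimator or a stated dichotomy would each give one. The supportable statement is that it is not defined as specified. Section 8.2.2 counts only four secondary endpoints as binary, and endpoints 2 to 5 are the proportions, so a dichotomy does not appear to be intended.

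The plan should be changed because this is the first step of the hierarchy and the correction is cheap.

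**What to change.** In the synopsis, Section 3.2 and Section 8.3.2:

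1. Define endpoint 1 as the distribution of the 90-day mRS (0 to 6, death = 6) compared between arms, in place of the shift from baseline.
2. In Section 8.3.2, replace the Cochran-Mantel-Haenszel sentence with a common odds ratio and 95% confidence interval from a proportional-odds model with treatment, pre-stroke mRS and the six randomisation factors as covariates. A named generalised Mantel-Haenszel estimator stratified by pre-stroke mRS would also do.
3. Replace the rule under which "the conclusion will be that the mRS shift is not proportional between the 2 devices". A proportional-odds model assumes proportionality, so that conclusion would contradict it. State which direction of the odds ratio favours Envi-SR, and read an interval that excludes 1 as a difference between arms in that direction.

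The cost is wording, one standard model and reliance on the proportional-odds assumption, which can be checked. All the data are already collected.
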